6.18. Annual Report Analyses

Based on regulatory requirements for the Development Safety Update Report (DSUR), reports will be produced (if not already available from the study CSR) for the reporting period covered by the DSUR.

6.19. Clinical Trial Registry Analyses

Additional analyses will be performed (if not already available from the study CSR) for the purpose of fulfilling the Clinical Trial Registry (CTR) requirements.

Analyses provided for the CTR requirements include the following:

Summary of AEs, provided as a dataset, will be converted to an XML file. Both serious adverse events (SAEs) and 'Other' AEs are summarized by treatment group and by MedDRA PT.

- An AE is considered 'Serious' whether or not it is a TEAE.
- An AE is considered in the 'Other' category if it is both a TEAE and is not serious. For each SAE and 'Other' AE, for each term and treatment group, the following are provided:
 - the number of participants at risk of an event,
 - the number of participants who experienced each event term, and
 - the number of events experienced.
- Consistent with www.ClinicalTrials.gov requirements, 'Other' AEs that occur in fewer than 5% of patients/subjects in every treatment group may not be included if a 5% threshold is chosen (5% is the minimum threshold).
- AE reporting is consistent with other document disclosures eg, the CSR, manuscripts, and so forth.

7. Unblinding Plan

Unblinding details are specified in a separated unblinding plan.

8. References

[CDC] Centers for Disease Control and Prevention. Growth Chart Training resources page. Accessed June 09, 2020. <https://www.cdc.gov/nccdpHP/dnpao/growthcharts/resources/sas.htm>.

Appendix 1. Study Visit Mapping for Pruritus NRS and Sleep-loss Diary and POEM

Pruritus NRS and sleep loss are collected as a daily diary; entries will be mapped to study week by the following:

Week	Start Day	End Day
Baseline	Date of First Injection ^a - 7	Date of First Injection-1
Week 1	Max(Date of First Injection, Week 2 Visit Date – 14)	Week 2 Visit Date – 8
Week 2	Week 2 Visit Date – 7	Week 2 Visit Date - 1
Week 4	Week 4 Visit Date – 7	Week 4 Visit Date – 1
Week 6	Week 6 Visit Date – 7	Week 6 Visit Date - 1
Week 8	Week 8 Visit Date – 7	Week 8 Visit Date - 1
Week 10	Week 10 Visit Date – 7	Week 10 Visit Date - 1
Week 12	Week 12 Visit Date – 7	Week 12 Visit Date – 1
Week 14	Week 14 Visit Date – 7	Week 14 Visit Date - 1
Week 16	Week 16 Visit Date – 7	Week 16 Visit Date – 1
Week 20	Week 20 Visit Date – 7	Week 20 Visit Date – 1
Week 24	Week 24 Visit Date – 7	Week 24 Visit Date – 1
Week 28	Week 28 Visit Date – 7	Week 28 Visit Date – 1
Week 32	Week 32 Visit Date – 7	Week 32 Visit Date – 1
Week 36	Week 36 Visit Date – 7	Week 36 Visit Date – 1
Week 40	Week 40 Visit Date – 7	Week 40 Visit Date – 1
Week 44	Week 44 Visit Date – 7	Week 44 Visit Date – 1
Week 48	Week 48 Visit Date – 7	Week 48 Visit Date – 1
Week 52	Week 52 Visit Date – 7	Week 52 Visit Date – 1

^a If date of first injection is missing, the randomization date will be used.

If multiple assessments on a single day are present, use the first assessment. If an assessment could be mapped to different weeks, it will be mapped to the earlier week. Derivation of the weekly mean scores for Pruritus NRS and Sleep-loss could be found in [Table KGAC.6.11](#). If at least 1 of the 7 days contains non-missing daily assessments, post-baseline weekly score will be calculated using prorated weekly average. If the range of 7 days are all missing daily assessments, then the weekly score is missing.

POEM are collected every week via eDiary, the visit week mapping will follow the following rule: the last collected POEM data before the visit date would be used, the evaluation window is

injection date - 7 to injection date -1 for baseline and assessment date - 7 to assessment date -1 for post baseline. For example if a patient gets an injection/assessment on the 14th, we would use the scale completed in between the 13th and the 7th.

Appendix 2. Details of Combining Estimates and Test Statistics for Categorical Endpoints with Multiple Imputation

Following the implementation of MCMC-MI imputation as specified in Section 6.4.1.1, the 25 data sets with imputations should be set together and sorted by imputation number. The following sections describe the processes for combining inferences for the individual imputed data sets into one inference for reporting. All calculations are performed in SAS software version 9.4.

Summarize Unadjusted Response Rate

The response rates, overall and by treatment arm, and their associated standard errors (SE) are computed for each imputed data set using PROC FREQ with the *riskdiff* option specified for the appropriate column in the TABLES statement. The response rates and SEs from the resulting output are combined across the 25 imputed data sets using PROC MIANALYZE, separately for each arm and the overall group.

Note that the estimate and 95% confidence interval (CI) bounds output by PROC MIANALYZE are percents (ie, they are in terms of the response rate). To obtain the number of responders, the estimated percentage is multiplied by the number of individuals in the analysis population and rounded to the nearest integer.

Compute Stratified Measures of Association

The common risk difference, common odds ratio (OR), and Cochran-Mantel-Haenszel (CMH) test statistic are computed for each imputed data set using PROC FREQ with the *riskdiff* option for the appropriate column (for risk difference) and the *cmh* option (for odds ratio and CMH test statistic) specified in the TABLES statement. Each of these analyses are stratified by geographic region, age group, and baseline disease severity via inclusion of these variables in the TABLES statement with the treatment and outcome variables.

Note that the PROC FREQ output corresponding to the Mantel-Haenszel method is used for the risk difference, and the output corresponding to the General Association statistic is used for the CMH statistic. PROC MIANALYZE is then called separately for each of these measures, with further details in the sections below.

Common Risk Difference

No transformation is necessary before using PROC MIANALYZE to combine the risk difference estimates and their associated SEs across the 25 imputed data sets. This procedure outputs an estimate of the common risk difference and the associated 95% CI bounds.

Common Odds Ratio

The OR from each imputed data set is first transformed using the natural logarithm. The SE for each log OR (SE_{lOR}) is derived from the OR 95% CI bounds (LB_{OR} , UB_{OR}) according to the following equation: $SE_{lOR} = (\ln(UB_{OR}) - \ln(LB_{OR}))/ (2 * 1.96)$. The log OR and derived SE are then combined using PROC MIANALYZE, which outputs a combined estimate of the log OR and the associated 95% CI. Finally, these measures can be exponentiated to transform them back to the OR scale.

Cochran-Mantel-Haenszel Test

The CMH test statistic (CMH) from each imputed data set is transformed using the Wilson-Hilferty transformation and standardized so that it has approximately a standard Normal distribution (Ratitch 2013). In particular, the transformed CMH statistic is computed as follows:

$$CMH_{WH} = \frac{\left(\frac{CMH}{df}\right)^{\frac{1}{3}} - \left(1 - \frac{2}{9*df}\right)}{\sqrt{\frac{2}{9*df}}}, \text{ where } df \text{ is the degrees of freedom of the CMH statistic. Then the}$$

SE for each CMH_{WH} is 1, and PROC MIANALYZE is used to output a combined estimate of the transformed CMH statistic. Note that the two-sided p-value output by PROC MIANALYZE is not used directly, but instead the one-sided p-value is computed manually using both the t statistic and two-sided p-value output by PROC MIANALYZE: if t statistic is greater than 0, then one-sided p-value is computed as half of the two-sided p-value; otherwise, the one-sided p-value is computed as 1 - half of the two-sided p-value. The resulting one-side p-value is reported as the pooled p-value for the CMH test.

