8.2.5. Pruritus

Pruritus will be assessed by the patient using a Pruritus Numerical Rating Scale (NRS). The Pruritus NRS is an 11-point scale used by patients to rate their worst itch severity over the past 24 hours with 0 indicating “No itch” and 10 indicating “Worst itch imaginable.” Assessments will be recorded daily by the patient using an electronic diary. Data will be transferred to the clinical database.

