8.2.6. Sleep-Loss

Sleep-loss due to pruritus will be assessed by the patient. Patients rate their sleep based on a 5-point Likert scale [0 (not at all) to 4 (unable to sleep at all)]. Assessments will be recorded daily by the patient using an electronic diary. Data will be transferred to the clinical database.

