6.1.2. General Considerations for Analyses During Induction Period

Induction Period starts after the first injection of study treatment at Baseline Visit (Day 1) and ends prior to the first injection of study treatment at Week 16 or the early termination visit (ETV) (between Day 1 and Week 16). For patients who are randomized but not dosed, the Induction Period starts on the date of randomization.

Baseline will be defined as the last available value before the first injection for efficacy and health outcome analyses. In most cases, this will be the measure recorded at Baseline Visit (Day 1). If the patient does not take any injection, the last available value on or prior to randomization date will be used. Change from baseline will be calculated as the visit value of interest minus the baseline value.

For Pruritus Numeric Rating Scale (NRS) and Sleep-Loss due to Pruritus collected via eDiary, the baseline period is the 7-day window prior to the first injection. A patient must have responses on at least 4 of 7 days to calculate a baseline weekly mean. If a patient has 3 or fewer responses, the baseline mean value will be considered missing. eDiary data for Pruritus NRS and Sleep-loss due to Pruritus are mapped to study visit per [Appendix 1](#).

For the safety analyses, the following baselines will be used. For safety analyses using a baseline period, the baseline period is defined as the time from Screening Visit to the date/time of the first injection in Induction Period.

- Treatment-emergent adverse events (TEAEs): baseline will be all results recorded during the baseline period.
- Treatment-emergent abnormal laboratory and vital signs results: baseline will be all results recorded during the baseline period.
- Change from baseline to last post-baseline observation or to each scheduled post baseline visit for laboratory and vital signs results: baseline will be the last scheduled non-missing assessment recorded during the baseline period.

The randomization to treatment groups is stratified by geographical region (US versus EU versus rest of world), age (adolescent patients 12 to <18 years versus adults ≥ 18 years) and baseline disease severity (IGA 3 versus 4) as described in Section [5.3](#). The countries will be categorized into geographic regions for analysis (Section [6.3](#)). Unless otherwise specified, the statistical analysis models for Induction Period will adjust for geographic region, age and baseline disease severity.

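### When the Week 2 visit is on time or early, the Week 1 itch mean includes the injection-day entry, whose 24-hour recall covers pre-dose hours, and this can hide 4-point responses

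*SAP*

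**What the plan says.** SAP Section 6.1.2 states that "the baseline period is the 7-day window prior to the first injection", and Appendix 1 gives its last day as "Date of First Injection-1". The injection-day entry is therefore not in baseline.

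Appendix 1 starts Week 1 at "Max(Date of First Injection, Week 2 Visit Date – 14" and ends it at "Week 2 Visit Date – 8". A post-baseline week needs only one daily score. If a day has two entries, the first is used.

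Protocol Section 8.2.5 has patients "rate their worst itch severity over the past 24 hours", and on timing says only "Assessments will be recorded daily by the patient using an electronic diary". SAP Section 6.1.2 has "Induction Period starts after the first injection of study treatment at Baseline Visit (Day 1".

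The 4-point itch response at Week 1, among patients with baseline NRS of at least 4, is a secondary endpoint in Protocol Table 1. SAP Section 6.4.1.1 derives it, and Section 6.4.1.2 gives it a tipping point analysis if its result is significant. It is not in the multiplicity-controlled lists of SAP Sections 6.6.1 and 6.6.2, where the itch responses are at Weeks 2, 4 and 16.

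**The concern.** Week 1 is the only row of Appendix 1 whose window can open on the day of first dosing. An entry made on that date is made either before the injection or less than 24 hours after it, so its recall period always covers some untreated time. The item asks for the worst itch, so a single pre-dose peak can set the score. Where there are two entries that day, the earlier one is kept.

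The mapping nevertheless counts this entry as fully post-baseline. It pulls the Week 1 mean towards baseline and raises the fall a patient must show on the remaining days. At stake is the earliest itch timepoint in the trial: some patients with a 4-point fall after dosing would be recorded as non-responders.

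**Working it through.** **Inputs.** The window limits come from SAP Appendix 1. The Week 2 visit window of plus or minus 3 days comes from Protocol Appendix 1. Day 1 is the day of first injection (Protocol Section 7), so an on-time Week 2 visit is Day 15.

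**Window.** Start = later of Day 1 and (visit day − 14); end = visit day − 8. On time: Day 15 − 14 = Day 1 and Day 15 − 8 = Day 7. That is seven days, which reproduces the 7-day week the plan averages over.

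**Threshold.** Let L be the number of entries in a full diary. If the Day 1 score equals the baseline mean and the other L − 1 entries fall by x on average, the Week 1 fall is x(L − 1)/L. Setting this to 4 gives x = 4L/(L − 1).

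| Week 2 visit | Week 1 days | Entries | Weight of Day 1 | Fall needed on other days |
|---|---|---|---|---|
| Day 12 (3 early) | 1–4 | 4 | 1/4 | 5.33 |
| Day 13 | 1–5 | 5 | 1/5 | 5.00 |
| Day 14 | 1–6 | 6 | 1/6 | 4.80 |
| Day 15 (on time) | 1–7 | 7 | 1/7 | 4.67 |
| Day 16 | 2–8 | 7 | 0 | 4.00 |
| Day 17 | 3–9 | 7 | 0 | 4.00 |
| Day 18 (3 late) | 4–10 | 7 | 0 | 4.00 |

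**Example, on time.** Baseline is 7.0, Day 1 is 7.0 and Days 2 to 7 are each 2.9, a fall of 4.1 on those days. The Week 1 mean is (7.0 + 6 × 2.9)/7 = 3.49. The recorded fall is 3.51, so the patient is a non-responder.

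**Low baselines, on time.** With Day 1 at baseline B and zero itch on Days 2 to 7, the fall is 6B/7. At B = 4 this is 3.43. It reaches 4 only when B is at least 28/6 = 4.67. A patient with baseline 4.00 to 4.66 is in the endpoint's population but cannot respond.

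**If Day 1 already shows part of the improvement.** With a fraction f of the later fall present on Day 1, the on-time requirement is 28/(6 + f): 4.48 for f = 0.25, 4.31 for f = 0.5 and 4.15 for f = 0.75.

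**Sparse diaries.** With Day 1 at baseline and m other entries, the requirement is 4(m + 1)/m: 6.0 for two others and 8.0 for one. A Day 1 entry alone cannot give a response.

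**Response rates, by assumption only.** The documents give no Week 1 itch response rate. Assume that falls on Days 2 to 7 are normal, visits are on time and Day 1 stays at baseline. With mean 1.5 and SD 2, the rate drops from P(Z ≥ (4 − 1.5)/2) = 10.6% to P(Z ≥ (4.67 − 1.5)/2) = 5.7%. Over means of 0.5 to 2.0 and SDs of 1.5 to 2.5, the loss runs from 0.7 to 6.9 percentage points.

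**The case against.** The strongest reply concerns timing. The plan does not say when in the day the diary is completed. A reader might infer that the Day 1 score is simply a pre-treatment score, or mostly one. The documents do not support that: an entry more than 12 hours after the injection looks back mostly on treated time. What can be said is that some pre-dose hours are always included. The figures of 4.67 and 5.33 assume a Day 1 score still at baseline and a full diary.

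A reader might also infer that the problem is general, or that it weakens the trial's evidence of early onset. Neither follows. Visits 1 to 3 days late already leave Day 1 out. The controlled early endpoints are itch response at Weeks 2 and 4, IGA response at Week 4 (FDA) and EASI-90 at Week 4 (EMA), and none uses the Week 1 window.

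Nor does the argument carry over in full to sleep loss. Protocol Section 8.2.6 says only that "Patients rate their sleep based on a 5-point Likert scale", with no recall period. Its responder rule is 2 points, and no Week 1 sleep-loss endpoint is listed by name.

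The SAP treats adverse events on the day of first dosing as post-treatment (Section 6.14.2), so counting Day 1 as post-baseline has a precedent. But that convention places an event by date. It does not answer the case of a score that looks back 24 hours.

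Two further points stand. The rule is identical in both arms and tends to shrink the difference, so it is conservative for the drug. SAP Version 5 was approved after the study team was unblinded to induction treatment, so changing an induction derivation now, in the direction that favours the drug, would be open to challenge.

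**Conclusion.** The point holds in a limited form, and it is minor. For on-time or early Week 2 visits, an itch entry that includes pre-dose hours makes up 1/7 to 1/4 of a full-diary Week 1 mean. If that score stays at baseline, the effective response threshold on the other days is 4.67 (on time) to 5.33 (3 days early) instead of 4.00. If Day 1 already shows half the later improvement, the on-time figure is 4.31.

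The window arithmetic follows from the documents. The size of the effect depends on the Day 1 score, the diary entries available and the mix of visit timings, none of which the documents give. The loss in response rate cannot be stated without assumed distributions. The consequence is limited to Week 1 results, chiefly a non-controlled secondary endpoint. The primary endpoints, Weeks 2, 4 and 16 and the controlled type I error are untouched.

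**What to change.** In SAP Appendix 1, start Week 1 at the later of the first-injection date plus 1 and the Week 2 visit date minus 14. Use the same window for sleep loss so that the two diary measures stay aligned. The fall needed on the counted days then returns to 4.00 for every visit timing, and windows after a late visit do not change.

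If the main derivation cannot be changed after induction unblinding, keep it and report the revised window as a labelled supplementary analysis of Week 1.

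The cost is one entry per affected patient: six remain when the visit is on time and three when it is 3 days early, against the SAP's minimum of one. The fix is not perfect, because a Day 2 entry made at an earlier clock time than the injection still recalls a few pre-dose hours.

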Appendix 3. Definition of Rescue Medications

This appendix provides the definition of rescue medications for this study, including topical and systemic treatments defined as follows:

1. Topical Atopic Dermatitis Treatment (including topical corticosteroids, TCI, and crisaborole)

Route of topical treatments includes: Topical and Transdermal.

Topical Corticosteroids (TCS): ATC code is D07

High Potency TCS: ATC codes: D07AC or D07AD

Low or moderate potency TCS: ATC code is D07, excluding D07AC or D07AD

Topical calcineurin inhibitor (TCI): Preferred Term includes: TACROLIMUS, PIMECROLIMUS

Crisaborole: Preferred Term includes: CRISABOROLE

2. Systemic Atopic Dermatitis Treatment (including systemic corticosteroids, immunosuppressant, biologics and phototherapy/photochemotherapy)

Route of systemic treatments administration includes: Oral, Intra-Arterial, Intramuscular, Intraperitoneal, Intravenous, Subcutaneous, Transdermal. (This condition applies to the following categories except for phototherapies.)

Systemic Corticosteroids: ATC code is H02

Immunosuppressant: Defined as: ATC2 is L04 or Preferred terms of Abrocitinib or Ruxolitinib

Biologics: Defined as following Preferred terms:

Infliximab, Infliximabum, Etanercept, Etanerceptum, Adalimumab, Adalimumabum, Certolizumab, Certolizumabum, Certolizumab pegol, Golimumab, Golimumabum, Ozoralizumab, Afelimumab, Afelimumabum, Tumor Necrosis Factor Alpha (TNF-) Inhibitors, Tabalumab, Tregalizumab, Anakinra, Basiliximab, Basiliximabum, Daclizumab, Daclizumabum, Tocilizumab, Tocilizumabum, Mepolizumab, Mepolizumabum, Rilonacept, Rilonaceptum, Ustekinumab, Canakinumab, Briakinumab, Fezakinumab, Sirukumab, Sarilumab, Lebrikizumab, Secukinumab, Olokizumab, Gevokizumab, Brodalumab, Ladarixin, Ixekizumab, Dupilumab, Tildrakizumab, Tildrakizumabum, Reslizumab, Reslizumabum, Guselkumab, Guselkumabum, Olamkicept, Fletikumab, Bimekizumab, Mirikizumab, Risankizumab, Abatacept, Ligelizumab, Vedolizumab, Belimumab, Nemolizumab, Tralokinumab, Omalizumab

Phototherapy or Photochemotherapy:

Programming search of medication name (actual term or preferred term) contains 'photo' then medicals to manually review to confirm whether the medication in question is indeed 'Phototherapy' or 'Photochemotherapy'

Signature Page for VV-CLIN-015694 v1.0

Approval	PPD an 19-Mar-2022 13:13:42 GMT+0000
----------	--

Signature Page for VV-CLIN-015694 v1.0

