HIV	human immunodeficiency virus
ICF	informed consent form
ICH	International Conference on Harmonization
IEC	independent ethics committee
IFN	interferon
Ig	immunoglobulin
IGA	Investigator Global Assessment
IL	interleukin
IRB	institutional review board
ITT	intent-to-treat
IV	intravenous
LDH	Lactic dehydrogenase
LOCF	last observation carried forward
LOR	loricrin
MCH	mean corpuscular hemoglobin
MCHC	mean corpuscular hemoglobin concentration
MCMC	Markov chain Monte Carlo
MCV	mean corpuscular volume
MedDRA	Medical Dictionary for Regulatory Activities
NRS	numerical rating scale
PFS-NSD	pre-filled syringe with a pre-assembled needle safety device
PIP	proximal interphalangeal
PK	pharmacokinetics
POEM	Patient Oriented Eczema Measure
PP	per protocol
PROMIS	Patient-Reported Outcomes Measurement Information System
PUVA	psoralen (P) and ultraviolet A (UVA) therapy
Q2W	every 2 weeks
Q4W	every 4 weeks
QoL	quality of life

Acronym	Term
RBC	red blood cells
SAE	serious adverse event
SAP	statistical analysis plan
SC	subcutaneous
SCORAD	SCORing Atopic Dermatitis
SD	standard deviation
SOC	system organ class
TB	tuberculosis
TCI	topical calcineurin inhibitor
TCS	topical corticosteroid
TEAE	treatment-emergent adverse event
TSLP	thymic stromal lymphopoietin
US	United States
USP	United States Pharmacopeia
VAS	visual analog scale
WBC	white blood cells
WHO	World Health Organization
WOCBP	women of childbearing potential

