4.2. Exclusion Criteria

Patients meeting any of the criteria below will be excluded from this study:

1. Participation in a prior lebrikizumab clinical study.
2. History of anaphylaxis as defined by the Sampson criteria ([Sampson, 2006](#)).
3. Treatment with topical corticosteroids, calcineurin inhibitors or phosphodiesterase-4 inhibitors such as crisaborole within 1 week prior to the baseline visit.
4. Prior treatment with dupilumab or tralokinumab.
5. Treatment with any of the following agents within 4 weeks prior to the baseline visit:
 - a. Immunosuppressive/immunomodulating drugs (e.g., systemic corticosteroids, cyclosporine, mycophenolate-mofetil, IFN- γ , Janus kinase inhibitors, azathioprine, methotrexate, etc.)
 - b. Phototherapy and photochemotherapy (PUVA) for AD.
6. Treatment with the following prior to the baseline visit:
 - a. An investigational drug within 8 weeks or within 5 half-lives (if known), whichever is longer.
 - b. B Cell-depleting biologics, including rituximab, within 6 months.
 - c. Other biologics within 5 half-lives (if known) or 16 weeks, whichever is longer.
7. Use of prescription moisturizers within 7 days of the baseline visit.
8. Regular use (more than 2 visits per week) of a tanning booth/parlor within 4 weeks of the screening visit.
9. Treatment with a live (attenuated) vaccine within 12 weeks of the baseline visit or planned during the study.
10. Uncontrolled chronic disease that might require bursts of oral corticosteroids, e.g., co-morbid severe uncontrolled asthma (defined by an ACQ-5 score ≥ 1.5 or a history of ≥ 2 asthma exacerbations within the last 12 months requiring systemic [oral and/or parenteral] corticosteroid treatment or hospitalization for > 24 hours).
11. Active chronic or acute infection requiring treatment with systemic antibiotics, antivirals, antiparasitics, antiprotozoals, or antifungals within 2 weeks before the baseline visit, or superficial skin infections within 1 week before the baseline visit.
NOTE: patients may be rescreened after infection resolves.
12. Evidence of active acute or chronic hepatitis (as defined by the Department of Health & Human Services Centers for Disease Control and Prevention) or known liver cirrhosis.
13. Diagnosed active endoparasitic infections or at high risk of these infections.

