6.3. Rescue Treatment for Atopic Dermatitis

Induction Period

The use of topical or systemic treatments for atopic dermatitis is prohibited from Baseline through Week 16 in this study. Patients who experience intolerable AD symptoms and require treatment should, preferably, be started on topical treatments (e.g., mid-potency TCS) prior to instituting systemic treatments for AD symptoms, in accordance with best practice.

If systemic rescue treatments (e.g., oral corticosteroids, phototherapy, cyclosporin, etc.) are required, study drug must be discontinued. The patient should continue to attend all study visits through Week 16 and be assessed for safety and efficacy according to the schedule of events.

Patients requiring topical or systemic rescue medication who complete the study through Week 16 will be eligible to continue to the Escape Arm after the Week 16 visit has been completed. Patients who required systemic rescue medication must wait for rescue medication washout (≥ 5 half-lives of the medication) prior to entering the Escape Arm.

Maintenance Period

Intermittent use of topical rescue medications for AD is permitted during the Maintenance Period. Patients who may require short-term systemic treatment for symptoms of AD during the Maintenance Period will be assessed on a case by case basis and must be discussed with the Medical Monitor prior to initiating treatment.

Escape Arm

Intermittent use of topical rescue medications for AD is permitted for patients who are in the Escape Arm. Patients who may require short-term systemic treatment for symptoms of AD during the Escape Arm will be assessed on a case by case basis and must be discussed with the Medical Monitor prior to initiating treatment. Patients requiring long-term systemic treatment for symptoms of AD in the Escape Arm (e.g., non-responders) must be discontinued from the study.

The Sponsor may supply the study sites with a mid-potency and a low-potency TCS that can be provided to patients for use, if needed (e.g., triamcinolone acetonide 0.1% cream and hydrocortisone 1% cream).

All topical and systemic treatments for AD must be captured in the eCRF.

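### SAP Appendix 3 defines rescue more narrowly than Protocol 6.3, which the estimands cite, so some phototherapy and some topical JAK or PDE-4 inhibitor use would go unflagged

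*SAP*

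**What the plan says.** **The event the estimands cite.** SAP 6.2.1 and 6.2.2 define the rescue intercurrent event by reference to Protocol 6.3. SAP 6.4.1.1 (for topical rescue), 6.4.1.3 and 6.4.2.2 do the same when they say what happens to the data. Protocol 6.3 bars every topical or systemic AD treatment from Baseline to Week 16, and on the systemic side it says: "If systemic rescue treatments (e.g., oral corticosteroids, phototherapy, cyclosporin, etc.) are required, study drug must be discontinued".

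**The event the programmers are given.** SAP 6.10.1 points to Appendix 3, which presents itself as the definition of rescue for the study. Its relevant rules are:

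- Phototherapy: "Programming search of medication name (actual term or preferred term) contains 'photo' then medicals to manually review".
- JAK inhibitors, under the systemic heading only: "Immunosuppressant: Defined as: ATC2 is L04 or Preferred terms of Abrocitinib or Ruxolitinib".
- Systemic routes: "Route of systemic treatments administration includes: Oral, Intra-Arterial, Intramuscular, Intraperitoneal, Intravenous, Subcutaneous, Transdermal".
- Topical routes: "Route of topical treatments includes: Topical and Transdermal". The only topical classes are corticosteroids (ATC D07), tacrolimus and pimecrolimus, and crisaborole.
- PDE-4 inhibitors: "Crisaborole: Preferred Term includes: CRISABOROLE".

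**The protocol's own vocabulary.** Exclusion criterion 5b uses an acronym: "Phototherapy and photochemotherapy (PUVA) for AD". The acronym list expands PUVA as "psoralen (P) and ultraviolet A (UVA) therapy". Protocol 4.2 and 6.1 refer to PDE-4 inhibitors as a class, with crisaborole as the example, and also name JAK inhibitors. The visit schedules in Protocol section 7 collect procedure and therapy information as well as medications.

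**The concern.** Two definitions of one intercurrent event are in force, the operational one is narrower, and nothing says which governs. Manual review confirms the hits of the phototherapy search but cannot recover its misses.

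The primary induction estimand treats rescue as failure and sets later values to baseline. If Appendix 3 does not flag a rescue, that step does not happen. Whatever was observed afterwards, including a response helped by the rescue, enters the analysis as if the patient were unrescued. The time to first rescue, the percentage rescued by visit and the flare summaries are affected directly.

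**Working it through.** **Step 1. Apply Appendix 3 literally to example records.**

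| Record | Flagged? | Reason |
|---|---|---|
| phototherapy, photochemotherapy | Yes, subject to review | Name contains *photo* |
| PUVA, UVA1, NB-UVB, narrowband ultraviolet B, light therapy | No, unless the preferred term contains *photo* | String absent |
| Any of these entered only as a procedure or therapy | Not covered as written | Rule searches medication names |
| Ruxolitinib or other JAK inhibitor, route Topical | No | Not a listed topical class; route fails the systemic condition |
| Ruxolitinib, route Transdermal | Yes, as systemic rescue | Listed by name; route allowed |
| Topical PDE-4 inhibitor other than crisaborole | No | Crisaborole only |

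Under Protocol 6.3 each of these, given for AD, is a topical or systemic AD treatment and so a rescue event.

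**Step 2. Trace a missed record through each analysis.**

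- *Topical, induction.* Protocol 6.3 and 8.7.2 require study drug to stop for systemic rescue, not topical. No second intercurrent event is triggered, so the observed Week 16 result stands in the primary, EASI-75, NRI and tipping-point analyses.
- *Phototherapy, induction.* Protocol 6.3 requires study drug to stop, so the case should surface as treatment discontinuation. NRI then gives non-response. The primary analysis gives the baseline value if the stop is recorded as lack of efficacy, and otherwise a missing value for MCMC-MI (SAP Table KGAC.6.3).
- *Systemic, maintenance.* Protocol 6.3 handles short-term systemic treatment case by case, so a recorded discontinuation need not follow. The primary maintenance estimand requires the baseline value (Table KGAC.6.4), and the time-to-loss endpoints censor at systemic rescue (Table KGAC.6.11). A miss loses both.
- *Topical, maintenance.* The primary estimand sets the values to missing, so a miss leaves observed data in their place. The hybrid supportive estimand uses observed data anyway. Only the composite/NRI analysis calls it failure.
- *Ruxolitinib coded Transdermal, maintenance.* It receives the systemic handling (baseline) instead of the topical handling (missing).

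**Step 3. Size per patient.** About 400 patients at 2:1 is taken as 267 and 133.

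- Lebrikizumab, induction: 100/267 = 0.37 points per missed rescue patient counted as a responder.
- Placebo, induction: 100/133 = 0.75 points.
- Maintenance, missed *systemic* rescue only, EASI-75 maintenance endpoint: 267 × 0.48 = 128 EASI-75 responders. One fifth are re-randomised to placebo, 128/5 = 25.6. One patient is 100/25.6 = 3.9 points.

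**Step 4. Assumed range for the primary endpoint.** The documents give no count of missed rescue, so the fractions below are assumptions. The planning inputs reproduce first: with 34.7% versus 7.7% and 96 versus 48 patients, continuity-corrected power is 95.2%, against the plan's claim of more than 95%. At 267/133 those rates give 93 and 10 responders, so the difference is 93/267 − 10/133 = 27.3 points. Resetting hidden-rescue responders to non-response gives:

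| Reset, lebrikizumab | Reset, placebo | Difference (points) |
|---|---|---|
| 3 (1%) | 0 | 26.2 |
| 5 (2%) | 0 | 25.4 |
| 13 (5%) | 0 | 22.4 |
| 0 | 3 (2%) | 29.6 |
| 13 (5%) | 7 (5%) | 27.7 |

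An unstratified Mantel-Haenszel test, (a − E)²/V with E = n₁m/N and V = n₁n₂m(N − m)/[N²(N − 1)], first loses significance when 55 lebrikizumab responders (55/267 = 20.6%) and no placebo responders are reset. Then a = 38, m = 48, E = 32.04 and V = 9.40, so the statistic is 3.78, below 3.84.

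**The case against.** The best defence has five parts.

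1. *Phototherapy in induction is caught another way.* A reader might infer that a missed phototherapy patient becomes an unrescued responder everywhere. The documents do not support that: the required stop of study drug makes the patient a non-responder in NRI and removes the observed value from the primary analysis. This stands. The residual risk is a stop recorded for another reason, where imputation could still produce a response, or a stop not made or not recorded.
2. *The 3.9-point figure does not carry over to topical agents.* This stands. Topical rescue in maintenance is not failure under the primary or hybrid supportive estimand.
3. *Other routes to detection exist.* The preferred term is searched too, so coding may recover some entries, and JAK agents coded Transdermal are caught if they are L04, abrocitinib or ruxolitinib. All AD treatments must be entered in the eCRF. Systemic treatment in maintenance must be discussed with the Medical Monitor first. SAP 5.3 makes induction rescue an input to re-randomisation. These points reduce the likely number, but none is stated to feed the imputation, and the dictionary and dataset layout are not given.
4. *Protocol 6.1 is not the rescue definition.* Agreed: its list concerns therapies for other conditions. The comparison here is with Protocol 6.3, and the class wording elsewhere only illustrates the narrowing.
5. *Nothing shows that such agents were available to these patients.* True; the only rescue products named for possible supply are topical corticosteroids. This limits frequency. It does not make the rule match the event.

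**Conclusion.** The point holds as a mismatch between a stated operational rule and the event the estimands cite. The induction topical case is the clearest: a patient who is a failure under the primary estimand can be analysed as an observed responder, worth about 0.37 points on lebrikizumab or 0.75 on placebo. Missed systemic rescue in maintenance affects the primary estimand and the censoring rules. Missed topical rescue there replaces required missing values with observed ones.

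A reader might go further and infer a bias in favour of lebrikizumab, or a threat to the primary result. Neither is supported. Misses concentrated on placebo would raise the placebo rate and shrink the difference, misses on lebrikizumab would do the opposite, and the documents do not show which is likelier. On the assumed 1% to 5% missed in the lebrikizumab arm alone, the IGA difference falls by about 1 to 5 points and remains significant. The conclusion assumes that Appendix 3 is applied as written, a 267/133 split and the planning rates. The number missed is unknown and probably small.

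**What to change.** Align Appendix 3 with Protocol 6.3 for analysis purposes:

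- Search both medication and procedure/therapy records, reported and coded terms, for *photo*, *PUVA*, *UVA*, *UVB*, *ultraviolet*, *psoralen* and *light therapy*, with medical review of the hits blinded to treatment.
- Add to the topical category any JAK inhibitor with a topical route, ruxolitinib included. Class it as topical when it is applied to the skin even if coded Transdermal. Add any topical PDE-4 inhibitor.
- State that Protocol 6.3 governs if the two definitions differ.

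SAP Version 5 was approved after the study team was unblinded to induction treatment. For induction, the reviewers should therefore have no access to assignments, and any patient whose rescue status changes should be reported under both definitions. The cost is a few lines in Appendix 3, a wider text search and a few more records to review.
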